#### **5.4.4 Handling of Withdrawals and Discontinuation of Treatment**

The primary reason for withdrawal from the study will be recorded on the Study Status data collection form. Subjects will be encouraged to complete an Early Termination Visit. Although subjects are free to withdraw at any time or may be withdrawn by the site principal investigator or appropriate sub-investigator at any time, subjects who receive at least one dose of study product will be encouraged to remain in the study for follow-up safety assessments.

Every attempt will be made to follow all protocol defined safety follow-up (solicited adverse events) to resolution or stabilization.

Subjects who withdraw, or are withdrawn or terminated from the study, or discontinue treatment will not be replaced.

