### 9.5.2 Individual Halting Rules (Termination of Study Product Administration)

Study product administration may be discontinued if any of the following criteria are met:

- Any clinical adverse event (AE), intercurrent illness, or other medical condition occurs that, in the opinion of the investigator, continued receipt of study product would not be in the best interest of the subject;
- New onset of illness or condition that meets exclusion criteria, at the investigator's discretion
- Inadequate clinical response that requires off-study antimicrobial therapy.
  - Subjects who require off-study antimicrobial therapy will be defined as having an inadequate clinical response.

Subjects may stop study drug treatment at any time of their own volition or at the advice of their treating provider or the study investigators. Subjects who stop study product for any reason will be regarded as having withdrawn from treatment but not as having withdrawn from the study (i.e, subjects will be asked to continue to participate in follow-up visits). All subjects with an inadequate clinical response will be referred to a non-study healthcare provider for evaluation and possible treatment outside of the clinical study. If requested, unblinding can occur if clinically indicated as determined by the treating clinician and the study's site investigator.

At the time of withdrawal, subjects will undergo an early termination visit if they are not willing to participate in the remaining follow-up visits.

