## 11 STATISTICAL CONSIDERATIONS

### 11.1 Study Hypothesis

The primary hypothesis is that placebo therapy is non-inferior in efficacy to azithromycin treatment in terms of clinical improvement rates when administered to adults with suspect lower respiratory tract infection (LRTI) and a procalcitonin level of  $\leq 0.25$  ng/mL. The primary time point of interest is 4 days after administration of study product (i.e. Day 5).

Null hypothesis:  $\pi_{\text{placebo}} - \pi_{\text{azithromycin}} \leq -12.5\%$ ,

Alternative hypothesis (non-inferiority):  $\pi_{\text{placebo}} - \pi_{\text{azithromycin}} > -12.5\%$ ,

where  $\pi$  represents the probability of clinical improvement at study Day 5. 12.5% is the non-inferiority margin used for this study.

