6.3.1. Intention-to-Treat Analysis (ITT) Population

The ITT population will include all subjects with PCT ≤ 0.25 ng/mL randomized to receive study product. The analyses on the ITT population will be performed per randomized treatment assignment. Subjects in the ITT population with missing values for clinical improvement or DOOR will be imputed using multiple imputation. Baseline variables and presence of fever at the timepoint of interest will be used in the multiple imputation model. For DOOR, daily maximum severity of solicited events and OCO will be used in the multiple imputation model.

Subjects randomized but not treated will also be analyzed in the ITT population. If fever and solicited events data are collected post-randomization for a subject that was not treated, that data will be used in the ITT analysis to assist in imputing the clinical improvement and DOOR. For subjects treated with study product, data collected post dose 1 will be used in the imputation model.

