6.5.4. Ordinal Clinical Outcome at D5V or D11V

The OCO at D5V is defined as follows:

If the subject died at any point of study participation, then OCO at D5V will be 8.

Else if the subject has missing clinical improvement at D5V then OCO at D5V will be missing.

Else if the subject did not have clinical improvement at D5V and was hospitalized then OCO at D5V will be 7.

Else if the subject did not have clinical improvement at D5V with ED, outpatient clinic, or urgent care visit but was not hospitalized then OCO at D5V will be 6.

Else if the subject did not have clinical improvement at D5V and did not have any medically attended events then OCO at D5V will be 5.

Else if the subject has missing most severe solicited event at D5V as defined in Section 6.5.3 then OCO at D5V will be missing.

Else if the subject had clinical improvement at D5V and a most severe solicited event of grade 3 at D5V then OCO at D5V will be 4.

Else if the subject had clinical improvement at D5V and a most severe solicited event of grade 2 at D5V then OCO at D5V will be 3.

Else if the subject had clinical improvement at D5V and a most severe solicited event of grade 1 at D5V then OCO at D5V will be 2.

Else if the subject had clinical improvement at D5V and did not experience any solicited event through D5V (i.e.; the most severe solicited event at D5V is of grade 0) then OCO at D5V will be 1.

The OCO at D11V is defined in a similar manner by replacing D5V by D11V in the above algorithm.

Note that in some cases OCO can be defined even if some components are missing. For instance, if a subject had record of receipt of study product and did not have clinical improvement at D5V, OCO at D5V would still be defined even if most severe solicited event at D5V was missing since the above algorithm doesn't take solicited events severity into account for OCO levels 5, 6, 7, and 8.

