7. STUDY SUBJECTS

7.1. Disposition of Subjects

Reasons for screening failures will be summarized in [Table 12](#). The completion status and reasons for early termination or treatment discontinuation will be summarized ([Table 8](#) and [Listing 2](#)). A subject could be discontinued early due to an AE (serious or non-serious), loss to follow-up, non-compliance with study, voluntary withdrawal, withdrawal at the investigator request, termination of the site by the sponsor, termination of the study by the sponsor, death, lack of eligibility at enrollment, inadequate clinical response, or becoming ineligible after enrollment.

Subject disposition and eligibility for analysis will be summarized in a CONSORT flow diagram ([Figure 1](#)).

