8. EFFICACY EVALUATION

All efficacy variables will be listed by subject. Data will be summarized by treatment group. Continuous efficacy variables will be summarized with the number of observations, mean, median, standard deviation, minimum, and maximum. Categorical efficacy variables will be summarized by number and percent in each category.

All statistical tests are performed at the $\alpha=0.05$ significance level. The primary hypothesis is a one-sided test but uses a two-sided 95% CI to make a conclusion about non-inferiority.

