8.4. Imputation of Missing Data

8.4.1. Multiple Imputation of Missing Values of Clinical Improvement on Day 5, Day 11, and Day 28

Primary and secondary analyses using the ITT population depend on multiple imputation of clinical improvement on D5V, D11V, and D28V. First, a table showing the number and percentage of missing data for clinical improvement on D5V, D11V, and D28V will be presented in Table 20. Regardless of the percent of missingness, multiple imputation will be used for all ITT analyses. Robustness of the multiple imputation

model will be assessed by tipping point analyses. The results of this sensitivity analyses will be provided in [Table 27](#) for D5V, [Table 28](#) for D11V and [Table 29](#) for D28V. In order to use the MI model to adjust for bias caused by missing data, we assume that data is missing at random (MAR).

For missing clinical improvement on D5V, D11V, or D28V, multiple imputations of missing clinical improvement on D5V, D11V, or D28V will be performed independently, and each subject will have their missing clinical improvement imputed independently of other subjects' imputations using a subject-specific imputation model. The pseudocode shown below details how missing data for clinical improvement for D5V (D11V or D28V) will be imputed using m multiply imputed datasets from linear models. The following covariates will be used non-missing for the MI model: treatment group, site indicators, age, gender, study day of D5V (centered at 5), presence of fever on Day 1, and presence of fever on D5V. The number of imputed, m , datasets will be chosen based on the average percent of missing data. Default value will be $m=20$ since sample size calculation assumed close to 20% drop-out rate.

As a first step to multiple imputation, an ordered list of variables to include in the subject-specific imputation model is constructed. Ordering is specified so that exact imputation results from final data are prespecified may be replicated in SAS (using seeds described below). The complete ordered list of variables for the imputation models for clinical improvement is below:

- Treatment Group (azithromycin is reference)
- Indicator of subject enrolled at the site with the second most number of subjects enrolled (binary indicator)
- Indicator of subject enrolled at the site with the third most number of subjects enrolled (binary indicator)

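### Deaths by Day 5, and study exits recorded as inadequate response without a qualifying visit record, have no failure rule in the primary endpoint and are imputed under MAR

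*SAP*

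**What the plan says.** Clinical improvement at the Day 5 visit (D5V) needs all four criteria of SAP 3.3.2. Criterion 4 fails a subject who has a medically attended visit or hospitalization for LRTI with a non-study antibiotic. SAP 6.5.1.4 derives it from the MAV form alone, in three ways:

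- A form showing an LRTI visit with an LRTI antibiotic makes the event present, whether or not D5V took place.
- A form without such an antibiotic makes it absent.
- With no completed D5V and no form, it is missing.

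D5V symptoms are read for the Visit 3 date only (SAP 6.5.1). For missing outcomes, SAP 6.3.1 says: "Subjects in the ITT population with missing values for clinical improvement or DOOR will be imputed using multiple imputation". The model in SAP 8.4.1 assumes missing at random, is fitted on ATP-5 subjects, and uses treatment, site, age, gender, visit day and fever.

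The reason for leaving is collected. Protocol 5.4.4 says: "The primary reason for withdrawal from the study will be recorded on the Study Status data collection form". SAP 7.1 has one combined list of reasons, which ends with "death, lack of eligibility at enrollment, inadequate clinical response, or becoming ineligible after enrollment". Protocol 9.5.2 adds: "Subjects who require off-study antimicrobial therapy will be defined as having an inadequate clinical response". Neither the endpoint derivation nor the imputation model uses the reason.

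Death is handled only in the ordinal clinical outcome (OCO) behind DOOR. SAP 6.5.4 tests it before it tests for missing improvement: "If the subject died at any point of study participation, then OCO at D5V will be 8".

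**The concern.** For these subjects the missing value is a consequence of the outcome. Someone who dies on Day 3, or leaves on Day 3 because the illness is not responding, did not improve by Day 5. The imputation nevertheless predicts that subject from people who took five doses and attended an in-person visit in window, with no term for why the subject left. In effect it awards a partial success.

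The direction matters in a non-inferiority trial. Protocol 2.3.1 names a lower improvement rate without azithromycin as the risk of placebo. If placebo subjects leave for non-response more often, the imputation hides some of the failures that would count against non-inferiority. SAP 8.1.1 lets the primary analysis alone decide that conclusion.

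**Working it through.** **1. Who is affected.** Three cases of a subject with no Visit 3, followed through SAP 6.5.1:

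- *Leaves after an LRTI visit with an antibiotic, MAV form submitted.* Criterion 4 fails, so this subject does not meet the definition of improvement.
- *Leaves the study, reason recorded as inadequate clinical response, no MAV form or a form without an LRTI antibiotic.* Criterion 4 is missing or absent and there are no D5V symptoms. Unless fever data decide the outcome, it is missing and imputed. An antibiotic recorded only as a concomitant medication does not trigger criterion 4.
- *Dies on or before D5V, no qualifying MAV form.* Clinical improvement is imputed, while the OCO is 8.

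The gap is the second and third cases. A related omission is that SAP 6.5.1 never says one failed component settles the composite when others are missing.

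**2. Inputs from the documents.** Protocol 11.1: "12.5% is the non-inferiority margin used for this study". SAP section 8: "The primary hypothesis is a one-sided test but uses a two-sided 95% CI to make a conclusion about non-inferiority", so one-sided 2.5%. SAP section 5 gives an improvement rate of 57.6% per arm, 560 in ATP-5 and 16.9% loss. The number randomized reproduces: 560 / (1 − 0.169) = 673.9, so 674, or 337 per arm.

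**3. Weight of one subject.** At the design rate, imputing one known failure adds 57.6 / 337 = 0.17 points to its arm; ten subjects add 1.71 points.

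**4. Bias at the margin.** Treatment is an imputation covariate, so each arm's leavers are imputed near their own arm's rate. With azithromycin at 57.6%, placebo at the margin is 57.6 − 12.5 = 45.1%.

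SE = √[(0.576 × 0.424 + 0.451 × 0.549) / 337] = 3.82 points.

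Bias = (placebo share × 45.1) − (azithromycin share × 57.6). One-sided error = 1 − Φ(1.96 − bias / 3.82). The shares are assumptions.

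| Assumed share, placebo vs azithromycin | Bias (points) | One-sided error |
|---|---|---|
| 3% vs 1% | 1.353 − 0.576 = 0.78 | 4.0% |
| 2% vs 1% | 0.902 − 0.576 = 0.33 | 3.0% |

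**5. Simulation check.** Setup: 337 per arm, 20 normal-linear imputations without rounding, Rubin's rules, 2,000 replicates, and a true difference of −12.5 points when affected subjects count as failures. Treatment was the only imputation covariate.

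| Affected, placebo / azithromycin | False non-inferiority, MAR | False non-inferiority, failure rule |
|---|---|---|
| 0 / 0 | 2.4% | 2.4% |
| 10 / 5 | 3.5% | 2.6% |
| 10 / 0 | 5.0% | 2.0% |
| 17 / 7 | 4.2% | 1.8% |
| 28 / 14 | 6.2% | 2.1% |

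The Monte Carlo standard error is about 0.35 points at 2.5% [√(0.025 × 0.975 / 2000)]. In the affected placebo scenarios the mean imputed value was 0.46 to 0.49. With 10 affected in each arm and equal observed rates (1,000 replicates) there was no bias, and non-inferiority was concluded in 89% of replicates under MAR and 90% under the failure rule.

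**The case against.** The strongest reply is that the plan already covers most of this. Protocol 9.5.2 ties inadequate response to needing off-study antimicrobials, and criterion 4 captures that through the MAV form without a completed D5V. Stopping study product is not leaving the study: such subjects are asked to stay in follow-up, and inadequate response is not among the named withdrawal reasons in Protocol 5.4.3. Before Visit 3, staff search the health record for visits, hospitalizations and antibiotics (Protocol 7.3.2). Leavers are offered an early termination visit at which endpoint components can be recorded (Protocol 7.3.5, SAP 6.5). Table 27 varies the success rate among missing subjects from 0% to 100% separately by arm, so its 0% placebo rows are harsher on placebo than a failure rule would be.

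Much of this stands, and it confines the point to the residual groups. It does not close the gap. SAP 6.5.1 has no rule for using early termination data, and the contact may be a telephone call about a week after withdrawal. Table 27 applies one rate to everyone missing in an arm and is a sensitivity analysis, so it does not correct the estimate that decides the trial.

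The death rules are also not strictly contradictory. OCO 8 covers death at any time on study and belongs to a different, ordinal endpoint. What stands is an omission in clinical improvement.

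**Conclusion.** The point holds for the two residual groups. Followed as written, the SAP gives a partial success to subjects whose failure is on record. The size depends on counts that the documents do not give. Under the assumed 3% versus 1%, the bias at the margin is about 0.8 points, or 6% of the 12.5-point margin (0.78 / 12.5), and the error is about 4.0%. Under 2% versus 1% it is about 0.3 points and 3.0%. With equal numbers affected and equal observed rates, the simulation found no bias. The change should be made, but nothing here shows that the primary conclusion would be wrong.

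Four stronger readings are tempting and not supported:

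- *That early leavers for non-response have no failure rule at all.* Criterion 4 is one, and it applies after early exit.
- *That leavers in both arms are imputed at about 58%, giving 0.02 × 57.6 = 1.15 points and 4.9% error for 3% versus 1%.* The SAP fixes no such rate. Error is evaluated at the margin, where placebo is imputed near 45%.
- *That the 16.9% loss measures the problem.* It is loss from ATP-5, which has many causes. All 57 subjects in one arm would give 57 × 57.6 / 337 = 9.74 points, which is only a ceiling.
- *That the SAP 8.4.1 pseudo-code discards observed failures outside ATP-5.* It merges imputed rows only with ATP-5 data and is unclear on this, but SAP 6.3.1 limits imputation to missing values.

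**What to change.** Add to SAP 6.5.1, ahead of any imputation:

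> If any observed component of clinical improvement at D5V fails, clinical improvement at D5V is No even when other components are missing. If clinical improvement at D5V would otherwise be missing and the subject died on or before D5V (planned Day 5 if no visit), or terminated the study by that day with recorded reason inadequate clinical response, clinical improvement at D5V is No. Observed D5V outcomes are not overridden.

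The last sentence protects a subject who stops study product but attends Visit 3. The rule does not require off-study antimicrobial therapy, since that would leave out the untreated non-responder whom criterion 4 also misses.

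In addition:

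- apply the parallel rule at D11V and D28V;
- impute only the subjects who are still missing;
- amend the SAP 8.4.1 pseudo-code so that observed outcomes outside ATP-5 stay in the ITT datasets;
- report the number set to failure by arm in Table 21.

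The cost is a short paragraph and one derivation step from records already planned for Listings 2 and 18. Improvement rates may fall slightly.

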6.3.2. According-to-Protocol (ATP) Cohorts

Subjects in an ATP analysis require no major protocol deviations and consumed 5 doses of study product by D5V. Subjects who miss a scheduled dose but resume the recommended dosing schedule within 24 hours remain eligible for ATP. As an exception, subjects who missed this window by at most 3 hours will be included in this population. What constitutes a major protocol deviation was assessed on a case-by-case basis by a DMID/VTEU/ARLG committee prior to any member of the committee being unblinded to treatment assignments. No major protocol deviations contributing to exclusion from ATP were identified. Subjects in an ATP analysis will be analyzed as treated. The ATP-5 (or ATP-11/ATP-28) populations will restrict subjects to those that meet the ATP requirements and furthermore completed their D5V (or D11V or D28V) in person

within the protocol defined time window and had sufficient data to define clinical improvement at D5V (or D11V or D28V). Missingness of DOOR will not exclude subjects from these ATP populations.

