### **7.3.2 Visit 3 (Day 5 + 3 days)**

The visit on Day 5 will represent the primary outcome assessment and will include an assessment of LRTI signs and symptoms. Also at Day 5, blood samples will be collected for repeat PCT testing. To permit evaluation of the secondary RADAR outcomes, all clinical parameters pertinent to the RADAR assessment will be ascertained at this time. This will be an in-person visit conducted at the study site. This visit can also be conducted in the subject's home.

Prior to this visit, study staff will make a preliminary assessment of the clinical response using the electronic health record to determine whether any of the following events have occurred after randomization and anticipated receipt of at least one dose of study agent.

- The subject had a medically attended visit to an ED, urgent care, or clinic;
- The subject was hospitalized during a separate clinical encounter following the enrollment encounter
- The subject received non-study, systemic antibiotic therapy

At the Day 5 visit, study staff will complete the following procedures:

- Assessment of clinical improvement including:
  - Review and collection of vital signs
  - Assessment and grading of LRTI symptoms
  - Occurrence of any medically attended visits
  - Receipt of any non-study systemic antibiotics
- Abbreviated physical examination to include general appearance and focused HEENT, neck, cardiopulmonary, and abdominal examinations;
- Review of the subject's memory aid
- Assess and record any solicited events and UADEs
- Review of memory aid and study product bottle (if available) to assess treatment compliance
- Obtain blood sample for PCT testing
- Review of study product bottle for drug accountability, if available;

If the subject develops signs or symptoms of pneumonia (including fever, increased work of breathing, increased/worsening cough, or new pulse oximetry reading  $\leq 90\%$ ) or develops a severe solicited event, the subject will be referred to his/her primary care provider or local urgent care center/ED. Study staff will assist in facilitating the follow up appointment. The study

staff will share all pertinent information related to the study with the treating clinician including treatment arm assignment if clinically indicated as determined by the treating clinician and the study's site investigator.

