### **7.3.3 Visit #4 (Day 11 + 3 days)**

Study subjects will be evaluated on Day 11 via telephone. Secondary and exploratory outcome measures will be assessed at this follow up. Study staff will complete the following procedures:

- Assessment of clinical improvement including:
  - Review and collection of temperature
  - Assessment and grading of LRTI symptoms
  - Occurrence of any medically attended visits
  - Receipt of any non-study systemic antibiotics
- Review of the subject's memory aid
- Assess and record any solicited events and UADEs

If the subject develops signs or symptoms of pneumonia (including fever, increased work of breathing, or increased/worsening cough) or develops a severe solicited event, the subject will be referred to his/her primary care provider or local urgent care center/ED. Study staff will assist in facilitating the follow up appointment. The study staff will share all pertinent information related to the study with the treating clinician including treatment arm assignment if clinically indicated as determined by the treating clinician and the study's site investigator.

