### **7.3.4 Visit # 5 Final Visit (Day 28 ± 2 days)**

Study subjects will be evaluated on Day 28 via telephone. Secondary outcome measures will be assessed at this follow up. Study staff will complete the following procedures:

- Assessment of clinical improvement including:
  - Review and collection of temperature
  - Assessment and grading of LRTI symptoms
  - Occurrence of any medically attended visits
  - Receipt of any non-study systemic antibiotics
- Assess and record any UADEs

If the subject develops signs or symptoms of pneumonia (including fever, increased work of breathing, or increased/worsening cough) or develops a severe solicited event, the subject will be referred to his/her primary care provider or local urgent care center/ED. Study staff will assist in facilitating the follow up appointment. The study staff will share all pertinent information

related to the study with the treating clinician including treatment arm assignment if clinically indicated as determined by the treating clinician and the study's site investigator.

The study staff will also review any new or changed con-commitment medications with the subject. A review of the medical record will also be done to recording results of clinical laboratory evaluations as specified in Section 8.2.1.

The exact date of the follow-up visit will be documented throughout the study.

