## **11.4 Final Analysis Plan**

The intention-to-treat (ITT) analysis population will consist of all randomized subjects. According-to-protocol (ATP) analysis populations will consist of subjects with no major protocol deviations regarding inclusion/exclusion criteria that consumed 5 doses of study product by Visit 3. The first dose of study drug should be taken within 24 hours of randomization. Subjects who miss a scheduled dose but resume the recommended dosing schedule within 24 hours remain eligible for ATP. However, in order for a subject to be eligible for the ATP-5 analysis, Visit 3 should be performed on or after the last day of study drug consumption while remaining within the 5+3 window. The ATP-5 analysis population will have the further restriction that the subjects must have completed an in-person Visit 3 within the protocol-defined time window. The ATP-11 analysis population will consist of the ATP analysis population with the further restriction that the subjects must have completed Visit 4 within the protocol-defined time window. The ATP-28

analysis population will consist of the ATP analysis population with the further restriction that the subjects must have completed Visit 5 within the protocol-defined time window.

Unless otherwise stated, all hypothesis tests and confidence intervals will be two-sided with  $\alpha=0.05$ . Statistical tests and confidence intervals will not correct for multiplicity.

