Table 71:	Listing of Unanticipated Adverse Device Effects - Safety Population	117
Table 72:	Summary of Vital Signs by Visit and Treatment Group	121
Table 73:	Number and Percentage of Subjects with Prior and Concurrent Medications by WHO Drug Classification and Treatment Group	122

9.5.1 Efficacy/Immunogenicity and Safety Measurements Assessed and Flow Chart**Table 4: Schedule of Events**

	Visit #1 Screening, Enrollment, & Randomization	Visit #2*	Visit #3	Visit #4*	Visit #5*	Early Termination Visits	Visit 5N (non-randomized Subjects)
Visit Number	01	02	03	04	05		5N ⁸
Visit Day ¹	Day 1	Day 3 +1	Day 5 +3	Day 11 +3	Day 28 ±2		Day 28+7
Obtain Informed Consent	X						
Assessment of Sociodemographic Data	X						
Randomization ²	X						
Dispense study drug ³	X						
Collection of study product bottle			X			X ⁷	
Review inclusion/exclusion criteria	X						
Assessment of medication compliance		X	X			X ⁷	
Assessment of Solicited AEs		X	X	X		X	
Assessment of UADEs		X	X	X	X	X	
Medical history ⁴	X		X	X	X	X	X ⁸
Physical exam ⁵	X		X			X ⁷	
Vital signs ⁶	X		X			X ⁷	
Assessment of LRTI signs and symptoms	X	X	X	X	X	X	
Concomitant medications ⁹	X	X	X	X	X	X	X ⁸
Distribute Memory Aid and Study-Related Materials	X						
Review Memory Aid		X	X	X		X ⁷	
Serum or Plasma PCT	X		X			X ⁷	
Nasopharyngeal Swab	X						
PAXgene Blood RNA (for future use, if consented)	X						

* Phone call assessment.

- 1 There will be a window around each of the scheduled follow-up assessments to allow for subject and staff flexibility.
2. Subjects with a PCT ≤ 0.25 ng/mL who satisfy the inclusion criteria with no exclusion criteria will be enrolled and randomized.
3. Study drug will be azithromycin or placebo.
4. Medical history will include: drug allergies, co-morbidities.
5. Physical exam will include: assessment of general appearance, a focused HEENT, neck, cardiopulmonary, and abdominal examination
6. Vital signs: temperature, pulse, blood pressure, respiratory rate, and pulse oximetry will be recorded. Care related exam findings and vital signs may be used.
7. These will be performed if indicated as part of the next regularly scheduled visit.
8. All data will be collected from a medical record review only. The subject will not be contacted.
9. All concomitant medications will be documented at Visit #1. Only non-study systemic antibiotic use will be documented at subsequent visits.

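### SAP 6.3.2 extends the in-person condition to the Day 11 and Day 28 telephone visits, contradicting SAP 6.3, the Table 9 shell and Protocol 11.4

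*SAP*

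**What the plan says.** SAP 6.3.2 defines the three visit-specific according-to-protocol populations in one sentence. Besides the general ATP requirements, subjects must have "completed their D5V (or D11V or D28V) in person", inside the visit window and with enough data to derive clinical improvement at that visit. The parenthesis carries the in-person condition to all three visits.

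The visits themselves are set out in the protocol:

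- Day 5 (Protocol 7.3.2): "This will be an in-person visit conducted at the study site". The same section also allows it in the subject's home.
- Day 11 (Protocol 7.3.3): "Study subjects will be evaluated on Day 11 via telephone".
- Day 28 (Protocol 7.3.4): "Study subjects will be evaluated on Day 28 via telephone".

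Protocol Appendix A and SAP Table 4 mark Visits 4 and 5 with an asterisk, explained in the SAP footnote as "Phone call assessment".

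Protocol 11.4 defines the same populations with different conditions. For ATP-5, "the subjects must have completed an in-person Visit 3 within the protocol-defined time window". For ATP-11, "the subjects must have completed Visit 4 within the protocol-defined time window", with nothing on visit mode. ATP-28 is defined in the same way for Visit 5.

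**The concern.** The population rule in SAP 6.3.2 asks for something that the visit schedule never provides. A programmer who builds the population flags from 6.3.2 gets a different result from one who uses the exclusion lists in SAP 6.3.

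ATP-11 and ATP-28 carry a large part of the later-timepoint plan:

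- ATP non-inferiority at Days 11 and 28 (SAP 8.2.3, Tables 24 and 26)
- antibiotic days (8.2.5, Tables 30 and 31)
- return visits, emergency department visits and hospitalisation (8.2.6, Tables 32 to 34)
- symptom improvement (8.2.7, Tables 35 and 36)
- the exploratory ATP-11 analyses in 8.3.3 to 8.3.8, including Tables 44, 45, 47, 51 and 59 to 61 and the ATP-11 row of Table 48

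Membership of these populations should not depend on which of two SAP sections is consulted.

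**Working it through.** The documents state no size for ATP-11 or ATP-28, so there is no figure to reproduce. The only ATP size given, 560, is for ATP-5. The check is a comparison of texts.

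**Step 1. Visit mode as scheduled.** D5V is in person; D11V and D28V are by telephone. Protocol 7.3.2 to 7.3.4, Protocol Appendix A and SAP Table 4 agree.

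**Step 2. Is in-person completion a condition of membership?**

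| Source | ATP-5 (D5V) | ATP-11 (D11V) | ATP-28 (D28V) |
|---|---|---|---|
| SAP 6.3.2 | Yes | Yes | Yes |
| SAP 6.3 exclusion lists | Yes | No | No |
| SAP Table 9 shell | Yes | No | No |
| Protocol 11.4 | Yes | No | No |

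All four agree on ATP-5. For ATP-11 and ATP-28, 6.3.2 stands alone against the other three.

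**Step 3. Combine the two.** Under 6.3.2 taken literally, the number of subjects followed as scheduled who qualify is 0 for ATP-11 and 0 for ATP-28, because no in-person D11V or D28V is scheduled. Under any of the other three sources, a telephone visit inside the window does not exclude the subject; the population size then depends on the data.

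**Step 4. Which reading fits the rest of the SAP?** The Listing 5 shell shows an example subject included in ATP-11 and ATP-28. It shows a second subject excluded from ATP-11 for not completing D11V and from ATP-28 for a visit outside the window. SAP 6.3 assigns each excluded subject one reason from its ordered lists, and those lists offer no reason that would cover a telephone D11V or D28V. The condition also has no measurement purpose at these visits: the D5V endpoint uses vital signs, whereas SAP 6.5.2 states that none were recorded for D11V or D28V.

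**Step 5. Do the other sources agree with each other?** On visit mode, yes. On data sufficiency, not fully. SAP 6.3 excludes subjects whose data cannot define clinical improvement at D11V; the Table 9 shell has no such row under ATP-11, though it has one under ATP-28; Protocol 11.4 has no such condition for any visit.

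**The case against.** The strongest reply is that this is a slip in merging three definitions into one sentence, and that the right rule is plain from SAP 6.3, Table 9, Listing 5 and Protocol 11.4. The consequences would also be limited. SAP 8.1.1 rests the non-inferiority conclusion on the primary analysis alone, Day 11 and Day 28 non-inferiority also have ITT analyses (SAP 8.2.2), and a literal application would show itself at once as tables with no subjects rather than bias a result unnoticed.

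Most of this stands. A reader might infer from 6.3.2 that the SAP requires empty ATP-11 and ATP-28 populations, on the ground that 6.3.2 is the governing definition. The documents do not support that: nothing ranks 6.3.2 above 6.3, and the Listing 5 example presupposes non-empty populations.

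A reader might also infer that the ITT imputations at Days 11 and 28 would lose their donors, because the SAP 8.4.1 pseudo-code imputes from ATP-5 subjects and says that its logic carries over to the later visits. The SAP does not say that ATP-11 and ATP-28 take the place of ATP-5 there, so this is not established.

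The reply does not remove the contradiction. Nothing ranks 6.3 above 6.3.2 either. An analyst who follows the workable rule departs from the text of 6.3.2, and the SAP preface requires deviations from the SAP to be described and justified in the study report.

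**Conclusion.** The point holds as an internal contradiction in the SAP, in which the wording of 6.3.2 is wrong for ATP-11 and ATP-28. The zero count is conditional: it needs 6.3.2 to be applied literally and in isolation, and it assumes that no Day 11 or Day 28 assessment was in fact done in person. The documents provide for none. What is affected is the set of according-to-protocol secondary and exploratory analyses at Days 11 and 28. The primary ITT analysis at Day 5, ATP-5 and the ITT definition are untouched. The sentence should be corrected because it decides who enters pre-specified analyses, but the point does not threaten the trial's main conclusion.

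**What to change.** Reword SAP 6.3.2 so that:

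- ATP-5 requires D5V completed in person inside its window;
- ATP-11 and ATP-28 require D11V or D28V, respectively, completed inside its window, with no condition on visit mode;
- each also requires enough data to derive clinical improvement at that visit.

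This matches the SAP 6.3 exclusion lists in full and Protocol 11.4 on visit mode. The new text should not require D11V or D28V to be by telephone. Neither SAP 6.3 nor Protocol 11.4 has that condition, and it would exclude an in-window assessment that happened to be done in person. While the section is open, add the missing insufficient-data row under ATP-11 in the Table 9 shell.

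The cost is one SAP sentence and one table-shell row, with no change to design or data collection.
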